[Part 2 of 2 of the document. The other parts are not shown.]

In addition, changes were made to clarify inclusion/exclusion criteria and study procedures, as follows:

- Contraception requirements in inclusion criteria

- Exclusion criteria to exclude patients on current treatment with probenecid to stay consistent with the prohibited treatments section
- Unblinded personnel at each study site will prepare the intravenous infusions of study drug and that the Sponsor will provide masking bags and blinded study personnel with administer the study drug
- Placebo is identical to active MHAA4549A in formulation, but not appearance
- The adverse event reporting period

Additionally, updates were made to the protocol, as follows:

- Contact information for reporting serious adverse events and non-serious adverse events of special interest
- Investigator follow-up instructions (Section 5.4.4)
- Poststudy adverse events reporting instructions (Section 5.5)
- Addition of publication of data and protection of trade secrets instructions (Section 9.5)
- Replacement of SOFA score calculations (Appendix 7)
- Addition of anaphylaxis precautions and management instructions (Appendix 10)

The Sponsor considers that changes in this amendment will increase the safety monitoring in this Phase 2b study without any significant impact on the scientific value of the trial, nor will they have any significant impact on the safety or mental or physical integrity of study patients.

RATIONALE FOR VERSION 5 (GLOBAL)

Protocol GV29216 was amended in Version 5 to add a high-dose arm (i.e., 8400 mg MHAA4545A) and to harmonize relevant regional feedback into a global amendment.

GV29216 will assess severely ill patients who may be infected with various influenza A strains and who have a higher viral burden and longer duration of viral shedding than the healthy volunteers in GV28985. This population may benefit from doses higher than 3600 mg. Therefore, the study design has been updated to include the addition of an 8400-mg treatment arm for further dose ranging. A Phase 1 study (GV29609) investigating the 8400-mg dose in healthy volunteers has completed dosing, and interim safety data is provided in the introduction.

The addition of the 8400-mg treatment necessitated an adjustment in the infusion rate to 120 minutes for MHAA4549A and placebo. In addition, to mitigate any concerns with safety monitoring, the study design was expanded to include an initial safety assessment by the Internal Monitoring Committee and the Scientific Oversight Committee of a sentinel safety cohort consisting of the first 30 patients enrolled or those patients enrolled during the first influenza season, whichever occurs first.

Version 5 also contains revisions to support the changes discussed above as well as updates to the background sections, as follows:

- The time to normalization end point was adjusted operationally based on investigator feedback to allow greater flexibility to be in line with local standard course of clinical care
- The sample size was adjusted to approximately 330 patients.
- The MHAA4549A dosing rationale was updated to support the 8400-mg dose.
- The background clinical safety and efficacy summaries were updated with the most current data concerning MHAA4549A. Preliminary safety data from the Phase 1 study (GV29609) was included in the clinical safety section to support the use of the 8400-mg treatment arm in this study (GV29216).
- Sections that previously required a protocol clarification letter were updated: use of unblinded personnel to prepare the IV infusions of study drug and the use of masking bags, SOFA score calculation, and anaphylaxis management instructions.
- The contraception language in the inclusion criteria was updated.
- PaO₂ conversion table included as an appendix to allow greater flexibility with standard clinical practice.

SUMMARY OF CHANGES: VERSION 5 AMENDMENT

This Version 5 amendment consolidates elements of two previous country-specific amendments and revises the study design to add a third treatment arm (i.e., 8400-mg treatment arm). The Summaries of Changes for previous amendments (i.e., Version 3 and Version 4) relevant to Version 5 are listed in this section for the convenience of sites that did not receive these versions of the protocol. However, only Version 5 revisions are presented as italicized text in the body of the protocol.

PROTOCOL SYNOPSIS

The protocol synopsis has been updated to reflect the changes to the protocol.

SUMMARY OF CHANGES: Version 3 (VHP Only)

SECTION 4.1.1: Inclusion Criteria

- Patients of reproductive potential must agree to use reliable means of contraception as described below as a minimum (adherence to more stringent local requirements may be required):
 - For female patients: Use of two acceptable methods of contraception throughout the trial, including the active treatment phase AND for *120 days 24 weeks* after the last dose of MHAA4549A. Acceptable methods of contraception include: intrauterine device, systemic hormonal contraception (oral or depot), vaginal ring, tubal ligation of the female partner, vasectomy of the male partner, use of latex condoms plus spermicide by the male partner, or cervical cap plus spermicide (where the spermicide could be foam, vaginal suppository, gel, cream, etc.). *Male partners who have had a vasectomy should have the appropriate post-vasectomy documentation available of the absence of sperm in the ejaculate. The vasectomized male partner should be the sole partner for that patient.*
 - For male patients: Use of condoms and refrain from sperm donation until for 30 days after dosing ~~when circulating drug levels remain high.~~

SECTION 4.1.2: Exclusion Criteria

- *Hypersensitivity to monoclonal antibodies or to the active substance or any excipients of MHAA4549A study drug*
- *Hypersensitivity to the active substance or to any excipients of oseltamivir*
- ~~Hypersensitivity to mAbs or any constituents of study drug~~

SUMMARY OF CHANGES: Version 4 (Russia Only)

GENERAL REVISIONS

The abbreviation “mAb” was removed and “monoclonal antibody” spelled out throughout. The list of abbreviations was updated.

SECTION 1.2.2: Clinical Safety Background

In GV28985, *the immunogenicity incidence rate among the 60 subjects who received MHAA4549A was 0%. One subject tested positive for anti-therapeutic antibodies (ATAs)* ~~This subject tested positive for ATA at baseline and post-baseline.~~ This *subject* was in the placebo group, which included 32 other subjects, resulting in an immunogenicity prevalence rate (ATA-positive rate at baseline) of 3.1% and an immunogenicity incidence rate (ATA titers post-baseline) of 3.1%, as well, within the placebo group. Overall, study GV28985 had an immunogenicity prevalence rate of 1%. ~~The immunogenicity incidence rate amongst the 60 subjects who received MHAA4549A was 0%.~~

SECTION 2.3: SECONDARY EFFICACY OBJECTIVES

- To determine changes in the extent and duration of viral shedding in ~~upper respiratory samples~~ *nasopharyngeal samples as a measure of the pharmacodynamic response*

SECTION 2.4: PHARMACOKINETIC OBJECTIVES

- To characterize the PK profile of MHAA4549A in [REDACTED] and/or [REDACTED]

SECTION 2.5: EXPLORATORY OBJECTIVES

- [REDACTED]
- [REDACTED]
- [REDACTED]
- [REDACTED]
- [REDACTED]

SECTION 3.1.1: Overview of Study Design

[REDACTED]

SECTION 3.2.5: Rationale for Biomarker Assessments

[REDACTED]

[REDACTED]

[REDACTED]

[REDACTED]

SECTION 3.3.3: Secondary Efficacy Outcome Measures

- Time to clinical ~~normalization~~ *resolution* of vital signs (3/5 criteria must be met):

SECTION 3.3.4: Pharmacokinetic Outcome Measures

- [REDACTED]

SECTION 3.3.5: Exploratory Outcome Measures

█

[REDACTED]

█

[REDACTED]

SECTION 4.1.1: Inclusion Criteria

- For female patients: Use of two acceptable methods of contraception throughout the trial, including the active treatment phase AND for *120 days* after the last dose of MHAA4549A. Acceptable methods of contraception include: intrauterine device, systemic hormonal contraception (oral or depot), vaginal ring, tubal ligation of the female partner, vasectomy of the male partner, use of latex condoms plus spermicide by the male partner, or cervical cap plus spermicide (where the spermicide could be foam, vaginal suppository, gel, cream, etc.). *Male partners who have had a vasectomy should provide the appropriate post-vasectomy documentation of the absence of sperm in the ejaculate. The vasectomized male partner should be the sole partner for that subject.*
- For male patients: Use of condoms *and refrain from sperm donation until 30 days after dosing* ~~when circulating drug levels remain high.~~

SECTION 4.1.2: Exclusion Criteria

- Hypersensitivity to monoclonal antibodies ~~mAbs~~ or to the active substance or any ~~constituents~~ excipients of MHAA4549A study drug
- Hypersensitivity to the active substance or to any excipients of oseltamivir
- Creatinine clearance ≤ 10 mL/min

SECTION 4.2: METHOD OF TREATMENT ASSIGNMENT AND BLINDING

Unblinded personnel (i.e., unblinded site pharmacist or other designated, qualified, unblinded study personnel) at each study site will prepare the IV infusions of study drug, as described in Section 4.3.3. The Sponsor will provide masking bags, and blinded study personnel will administer the study drug. The other parties who are involved in the conduct of the study (i.e., patients and blinded site personnel) will remain blinded to patient-specific treatment assignments until the final database lock after the completion of the study.

SECTION 4.3.1.1: MHAA4549A and Placebo

Placebo is identical to active MHAA4549A in formulation ~~and appearance~~ but does not contain active drug substance.

SECTION 4.3.2.1: MHAA4549A and Placebo

The randomization of patients will be managed by a central IxRS. All patients will be randomly assigned to receive either a single dose of MHAA4549A 3600 mg IV or placebo IV at a 1:1 ratio. ~~Osetamivir will be dispensed via~~ *Osetamivir 75 mg and 150 mg will be supplied via IxRS.*

A single dose of MHAA4549A or placebo will be delivered by IV infusion following dilution in 0.9% normal saline over approximately ~~60~~120 minutes. Compatibility testing has shown that MHAA4549A is stable when diluted in 0.9% normal saline in a polyvinylchloride *bag*, polyolefin bag, or ethylene vinyl acetate bag (EVA), at ~~or above a combined total concentration~~ *concentrations* of 0.24 mg/mL up to 27.0 mg/mL.

SECTION 4.3.2.2: Osetamivir-Neuraminidase Inhibitor (NAI)

Osetamivir 75 mg and 150 mg will be supplied via IxRS. For renally impaired patients requiring the 30-mg dose strength, the Sponsor will supply osetamivir or reimburse sites for osetamivir per local regulations.

SECTION 4.6.5:

[REDACTED]

SECTION 4.6.6:

[REDACTED]

SECTION 4.6.10: Laboratory, Biomarker, and Other Biological Samples

[REDACTED]

[REDACTED]

[REDACTED]

SECTION 5.2.1: Adverse Events

Adverse events will be monitored throughout the entire study (enrollment through Day 60 or Early Discontinuation). ~~If clinically significant signs or laboratory values are observed in a study participant, the investigator should repeat an assessment at the earliest opportunity. Only those events or laboratory values that exceed the level of clinical significance upon the repeat assessment will be considered an adverse event.~~

SECTION 5.3.1: Adverse Event Reporting Period

After initiation of study drug, all adverse events, regardless of relationship to study drug, will be reported until the Day 60 visit or Early Discontinuation visit. After this period, the investigator *should report any serious adverse events that are believed to be related to prior study drug treatment* ~~is not required to actively monitor patients for adverse events; however, the Sponsor should be notified if the investigator becomes aware of any death or other serious adverse event that occurs after discharge, regardless of causality. The Sponsor should also be notified if the investigator becomes aware of a congenital anomaly/birth defect in a subsequently conceived offspring of a female patient exposed to study drug (see Section 5.5).~~

SECTION 5.3.5.4: Abnormal Laboratory Values

It is the investigator's responsibility to review all laboratory findings. Medical and scientific judgment should be exercised in deciding whether an isolated laboratory abnormality should be classified as an adverse event. *Investigators should promptly repeat any abnormal assessment or clinically significant laboratory result. Only those findings that remain clinically significant upon a repeat assessment will be considered adverse events.*

SECTION 5.4.1: Emergency Medical Contacts

Medical Monitor: [REDACTED]
Telephone Nos.: US Mobile-Office [REDACTED]
US Office-Mobile [REDACTED]

SECTION 5.4.2.1: Events That Occur Prior to Study Drug Initiation

A paper Serious Adverse Event / *Adverse Event of Special Interest* Reporting Form ~~and fax cover sheet~~ should be completed and faxed *or scanned and emailed* to the Sponsor's Safety Risk Management department or its designee immediately (i.e., no more than 24

hours after learning of the event), using the ~~fax numbers~~ *contact information* provided below per region:

Region	Fax Number	Email Address
Asia Pacific	[REDACTED]	[REDACTED]
Europe	[REDACTED]	
Latin America	[REDACTED]	
North America	[REDACTED]	

Asia Pacific: [REDACTED]

Europe: [REDACTED]

Latin America: [REDACTED]

North America: [REDACTED]

SECTION 5.4.2.2: Events that Occur after Study Drug Initiation

In the event that the EDC system is unavailable, a paper Serious Adverse Event Reporting Form and fax cover sheet should be completed and faxed *or scanned and emailed* to Safety Risk Management or its designee immediately (i.e., no more than 24 hours after learning of the event), using the ~~fax numbers~~ *contact information* provided to investigators (see ~~fax numbers provided in~~ Section 5.4.2.1). Once the EDC system is available, all information will need to be entered and submitted via the EDC system.

SECTION 5.4.3.1: Pregnancies in Female Patients

In the event that the EDC system is unavailable, a paper Clinical Trial Pregnancy Reporting Form and fax cover sheet should be completed, ~~and~~ faxed, *or scanned and emailed* to Safety Risk Management or its designee immediately (i.e., no more than 24 hours after learning of the pregnancy), using the ~~fax numbers~~ *contact information* provided to investigators (see ~~fax numbers provided in~~ Section 5.4.2.1). Once the EDC system is available, all information will need to be entered and submitted via the EDC system.

SECTION 5.4.4: Investigator Follow Up

During the study period, resolution of adverse events (with dates) should be documented on the Adverse Event eCRF and in the patient's medical record to facilitate source data verification. ~~If, after follow up, return to baseline status or stabilization cannot be established, an explanation should be recorded on the Adverse Event eCRF and the Investigator document a discharge plan.~~

SECTION 5.5: POSTSTUDY ADVERSE EVENTS

The Sponsor should be notified if the investigator becomes aware of any serious adverse event that occurs after the end of the adverse event reporting period, defined as 60 days after the last dose of study drug (see Section 5.3.1), if the event is believed to be related to prior study drug treatment.

The investigator should report these events directly to Roche or its designee, either by faxing or by scanning and emailing the Serious Adverse Event / Adverse Event of Special Interest Reporting Form using the fax number or email address provided to investigators (refer to site binder). ~~At the time of study completion or study discontinuation, the investigator should instruct each patient to report to the investigator any subsequent adverse events that the patient or their personal physician believes could be related to prior study drug treatment or study procedures.~~

~~The investigator is not required to actively monitor patients for adverse events after the end of the adverse event reporting period (defined as 60 days after the dose of study drug). However, the Sponsor should be notified if the investigator becomes aware of any death, other serious adverse event, or non-serious adverse event of special interest occurring after the end of the adverse event reporting period, regardless of causality. The Sponsor should also be notified if the investigator becomes aware of the development of cancer or a congenital anomaly/birth defect in a subsequently conceived offspring of a female patient or a female partner of a male patient exposed to study drug.~~

SECTION 6.4.2: Secondary Efficacy Endpoints

- Median duration of viral shedding in ~~upper respiratory samples~~ *nasopharyngeal samples*

SECTION 9.5: PUBLICATION OF DATA AND PROTECTION OF TRADE SECRETS

*Regardless of the outcome of a trial, the Sponsor is dedicated to openly providing information from the trial to healthcare professionals and to the public, both at scientific congresses and in peer-reviewed journals. The Sponsor will comply with all requirements for publication of study results. For more information, refer to the Roche Global Policy on Sharing of Clinical Trials Data at the following website:
<http://www.rochetrials.com/pdf/RocheGlobalDataSharingPolicy.pdf>*

The results of this study may be published or presented at scientific congresses. For all clinical trials in patients involving an IMP for which a marketing authorization application has been filed or approved in any country, the Sponsor aims to submit a journal manuscript reporting primary clinical trial results within 6 months after the availability of the respective clinical study report. In addition, for all clinical trials in patients involving an IMP for which a marketing authorization application has been

filed or approved in any country, the Sponsor aims to publish results from analyses of additional endpoints and exploratory data that are clinically meaningful and statistically sound.

The investigator must agree to submit all manuscripts or abstracts to the Sponsor prior to submission for publication or presentation. This allows the Sponsor to protect proprietary information and to provide comments based on information from other studies that may not yet be available to the investigator.

In accordance with standard editorial and ethical practice, the Sponsor will generally support publication of multicenter trials only in their entirety and not as individual center data. In this case, a coordinating investigator will be designated by mutual agreement.

Authorship will be determined by mutual agreement and in line with International Committee of Medical Journal Editors authorship requirements. Any formal publication of the study in which contribution of Sponsor personnel exceeded that of conventional monitoring will be considered as a joint publication by the investigator and the appropriate Sponsor personnel.

Any inventions and resulting patents, improvements, and/or know-how originating from the use of data from this study will become and remain the exclusive and unburdened property of the Sponsor, except where agreed otherwise.

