Oseltamivir (Tamiflu®) is an influenza NAI indicated for treatment of acute, uncomplicated influenza. *The Sponsor will provide oseltamivir capsules for up to a 10-day treatment course.*

SECTION 4.3.2.1: MHAA4549A and Placebo

The randomization of patients will be managed by a central IxRS. All patients will be randomly assigned to receive either a single dose of MHAA4549A 3600 mg IV or MHAA4549A 8400 mg IV or placebo IV at a 1:1:1 ratio.

A single dose of MHAA4549A or placebo will be delivered by IV infusion following dilution in 0.9% normal saline over approximately ~~60~~120 minutes. Compatibility testing has shown that MHAA4549A is stable when diluted in 0.9% normal saline in a polyvinylchloride bag, polyolefin bag, or ethylene vinyl acetate bag (EVA), at ~~or above a combined total concentration~~concentrations of 0.24 mg/mL up to 27.0 mg/mL.

SECTION 4.3.2.2: Oseltamivir-Neuraminidase Inhibitor (NAI)

The Sponsor will *supply* oseltamivir (Tamiflu®) for this study for up to a 10-day course. ~~Dosage and administration should follow local prescribing information for oseltamivir.~~ Either 75 mg or 150 mg of oseltamivir will be administered twice daily as described in Table 2. Capsules can be opened and the granules administered via nasogastric tube, if required. *Doses should be captured in the eCRF.*

SECTION 4.4: POST-TRIAL ACCESS TO MHAA4549A

The Roche Global Policy on Continued Access to Investigational Medicinal Product is available at the following Web site:

http://www.roche.com/policy_continued_access_to_investigational_medicines.pdf

SECTION 4.5.2: Prohibited Therapy

Use of other NAIs, including but not limited to ~~oral~~ oseltamivir, ~~inhaled~~ zanamivir, ~~oral~~ ribavirin, ~~laninimivir~~, and peramivir, are prohibited during the study, but allowed up to ~~3 days (a total of 6 doses)~~ (3 doses for peramivir) in the period from onset of symptoms and prior to study treatment as outlined in the exclusion criteria. *Patients must start standard-of-care oseltamivir no later than 8 hours after completion of MHAA4549A administration. If oseltamivir resistance is highly suspected or identified during treatment or if oseltamivir route of administration challenges are encountered, then, following discussion with the Sponsor's medical representative, an alternative NAI to oseltamivir may be used.*

SECTION 4.6.2: Diagnostic Testing for Enrollment

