- To measure the frequency and severity of the following secondary complications of influenza:
 - Pneumonia (hospital acquired pneumonia [HAP]/ ventilator acquired pneumonia [VAP])
 - Exacerbations of chronic lung disease
 - Myocarditis
 - Acute respiratory distress syndrome (ARDS)
 - Otitis media
 - Other related complications
 - Readmission rates at 30 and 60 days after study treatment
- To measure duration of positive pressure ventilation (PPV)
- To measure readmission rates

Pharmacokinetic Objectives

The major pharmacokinetic (PK) objective for this study is as follows:

- To characterize the PK profile of MHAA4549A in serum

The exploratory PK objectives for this study are as follows:

- [REDACTED]
- [REDACTED]

Exploratory Objectives

The exploratory objectives for this study are as follows:

- [REDACTED]
- [REDACTED]
- [REDACTED]
- [REDACTED]
- [REDACTED]
- [REDACTED]
- [REDACTED]
- [REDACTED]

Study Design

Description of Study

This is a Phase 2b (GV29216), randomized, double-blind, placebo-controlled study designed to assess the safety and clinical activity of a single intravenous (IV) dose of 3600 mg MHAA4549A

or a single IV dose of 8400 mg MHAA4549A in hospitalized patients with severe influenza A in combination with oseltamivir versus a comparator arm of oseltamivir with placebo. *A Sponsor-approved influenza test that includes influenza antigen test or influenza polymerase chain reaction (PCR) test must be used to diagnose influenza A infection for study eligibility.*

Initially, GV29216 enrolled and randomized patients into two treatment groups: a single IV dose of 3600 mg of MHAA4549A with oseltamivir or a single IV dose of placebo with oseltamivir.

Patients will be randomized 1:1:1 into three treatment groups: a single IV dose of 3600 mg of MHAA4549A with oseltamivir, a single IV dose of 8400 mg of MHAA4549A with oseltamivir, or a single IV dose of placebo with oseltamivir.

All patients must begin study drug infusion within 48 hours of hospital admission; therefore, screening must be completed within this window. All patients will receive oseltamivir for a minimum of 5 days (10 doses), starting on Day 1 beginning no later than 12 hours after completion of study drug administration. All patients will be followed for 60 days from the time of study drug administration.

Number of Patients

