4.2 METHOD OF TREATMENT ASSIGNMENT AND BLINDING

The randomization of patients will be managed by a central Interactive Voice and Web Response System (IxRS) through use of a dynamic hierarchical algorithm which includes a random component. The treatment assignments will be unblinded to selected Sponsor personnel to facilitate ongoing monitoring of safety and tolerability, including members of the IMC and SOC.

All patients will be randomly assigned to receive 3600 mg MHAA4549A, 8400 mg MHAA4549A, or placebo at a 1:1:1 ratio stratified by country, whether patient is on PPV versus supplemental O₂ at randomization, and whether the patient has suspected or

confirmed bacterial pneumonia vs no bacterial pneumonia at randomization. Initially GV29216 randomly assigned patients to receive either 3600 mg MHAA4549A, or placebo at a 1:1 ratio. The updated randomization scheme takes into account the numbers already allocated to these two arms and strata prior to allocating to the three arm design so that by the end of the study there will be an approximate 1:1:1 allocation between the three arms.

All patients will receive oseltamivir (as described in [Table 2](#)) for a minimum of 5 days. Treatment for longer than 5 days is permitted based on local investigator discretion.

Unblinded personnel (i.e., unblinded site pharmacist or other designated, qualified unblinded study personnel) at each study site will prepare the IV infusions of study drug, as described in [Section 4.3.3](#). The Sponsor will provide masking bags and blinded study personnel will administer the study drug. The other parties who are involved in the conduct of the study (i.e., patients and blinded site personnel) will remain blinded to patient-specific treatment assignments until the final database lock after the completion of the study.

Bioanalytical laboratory personnel responsible for performing PK assays will be unblinded to patients' treatment assignments to identify appropriate PK samples to be analyzed. Samples from patients assigned to the comparator arm will not be analyzed except by request (e.g., to evaluate a possible error in study drug administration).

While PK samples must be collected from patients assigned to the comparator arm to maintain the blinding of treatment assignment, PK assay results for these patients are generally not needed for the safe conduct or proper interpretation of this trial.

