4.3.2 Dosage, Administration, and Compliance

4.3.2.1 MHAA4549A and Placebo

Administration of MHAA4549A or placebo will be performed in a setting with emergency medical equipment and personnel who are trained to monitor for and respond to medical emergencies. A qualified physician or medically qualified designee will be on site during study drug administration for all patients.

A single dose of MHAA4549A or placebo will be delivered by IV infusion following dilution in 0.9% normal saline over approximately 120 minutes. Study drug should be delivered using a 0.20- to 0.22- μ m in-line filter. Compatibility testing has shown that MHAA4549A is stable when diluted in 0.9% normal saline in a polyvinylchloride bag, polyolefin bag, or ethylene vinyl acetate bag (EVA), at concentrations of 0.24 mg/mL up to 27.0 mg/mL. Study drug must be administered within the treatment window outlined in [Section 3.1.1](#). Further detailed instructions for preparation of study drug can be found in the Pharmacy Manual.

Subjects who experience a moderate-to-severe infusion-related reaction should have their infusion stopped. The infusion should not be restarted. The infusion will be discontinued in the event that the subject experiences a serious reaction and further dosing of subjects will be halted until the safety of the drug is assessed.

There are no recommended dosage modifications for MHAA4549A since it is a single infusion. Any overdose or incorrect administration of study drug should be noted on the Study Drug Administration electronic Case Report Form (eCRF). AEs associated with an overdose or incorrect administration of study drug should be recorded on the Adverse Event eCRF. General supportive measures will be taken to manage any AEs associated with overdose. Patients experiencing such AEs will be followed up clinically until the event has resolved.

Trained clinical site staff responsible for adequate and accurate study drug administration, accounting, and management will administer study drugs to patients. Study drug preparation and dosing instructions will be provided to each site. The exact times of study drug administration will be recorded in the relevant dispensing/administration logs and patient's source notes. Any noncompliance or problems with study drug administration will be recorded in the patient's source notes and reported to the Sponsor if appropriate.

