6.5 SAFETY ANALYSES

The safety analyses will include all randomized patients who received study drug, with patients grouped according to the treatment actually received. Safety parameters to be evaluated include AEs (including deaths, SAEs, discontinuations due to AEs, and the incidence and severity of AEs), clinical laboratory tests, vital signs (including SpO₂ measurements), and ECGs.

All collected AE event data will be listed by study site and patient number. All AEs that occur on or after treatment on Day 1 will be summarized for each treatment group by mapped term, appropriate thesaurus levels, body system, and event within each body system, and toxicity grade. In addition, all SAEs, including deaths, will be listed separately and summarized. SAEs caused by a protocol mandated intervention (e.g., invasive procedures such as biopsies, discontinuation of medications) that occur between consent and first dose of study medication will be listed separately.

Laboratory data with values outside of the normal ranges will be identified. In addition, select laboratory data will be summarized by treatment group using descriptive summary statistics.

The absolute and percentage changes from baseline in vital sign parameters will be computed, and changes deemed clinically significant by the Investigator will be noted. Appropriate descriptive summary statistics will be provided for all vital sign parameters

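### Section 6.5 groups acute safety by treatment alone, so 8400 mg (always planned at 120 minutes) is set against 3600-mg and placebo groups that may mix 60- and 120-minute infusions

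*Combined protocol and SAP*

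**What the plan says.** The Version 5 rationale ties the change to the new arm: "The addition of the 8400-mg treatment necessitated an adjustment in the infusion rate to 120 minutes for MHAA4549A and placebo". The Version 5 (Global) change log for Section 4.3.2.1 shows the old and new times: "following dilution in 0.9% normal saline over approximately ~~60~~120 minutes". The Version 4 (Russia only) log lists the same change while randomization was still 3600 mg v placebo, 1:1. The current Section 4.3.2.1 delivers every arm "over approximately 120 minutes".

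A two-arm stage did take place. The current synopsis says: "Initially, GV29216 enrolled and randomized patients into two treatment groups". Section 4.2 confirms that at first "GV29216 randomly assigned patients to receive either 3600 mg MHAA4549A, or" placebo at 1:1, and that the updated scheme allows for those patients so that the final allocation is roughly 1:1:1.

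On analysis, Section 6.5 says "The safety analyses will include all randomized patients who received study drug, with" each patient placed under the treatment received. Neither Section 6 nor 6.5 adds a factor for infusion duration or protocol version. Section 6 presents each dose, and the two combined, against standard of care, without formal testing. The season subgroup in Section 6.4.3 covers the primary and selected secondary efficacy endpoints, not safety.

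Section 1.3.2 names infusion-related reactions as a potential risk, and Section 5.2.3 makes suspected cases within 24 hours an adverse event of special interest (AESI).

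**The concern.** Infusion speed could plausibly affect acute reactions, and it changed partway through enrollment for two arms only. The 8400-mg arm opened with the 120-minute infusion. The 3600-mg and placebo arms can carry patients dosed under both plans. A table pooled by treatment then compares 8400 mg at one speed with a mixture.

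At stake is the descriptive reading of acute tolerability by dose. Section 1.3.1 says the third arm was added for more dose-response information, so readers will set the two doses side by side. If faster infusion of active drug raises risk, the pooled 3600-mg rate sits above its 120-minute rate, and the excess at 8400 mg looks smaller than it is.

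The amendment logs serve here only as history. The gap is in the current Section 6.5.

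**Working it through.** **Inputs from the documents.** About 330 patients, and about 110 per arm (Section 6.1); 330/3 = 110 reproduces the stated figure. Durations are about 60 and about 120 minutes (change logs; Section 4.3.2.1). No infusion-reaction rate, no two-arm patient count and no effect of speed is stated.

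**Planned dose rates.** 3600/60 = 60 mg/min; 3600/120 = 30 mg/min; 8400/120 = 70 mg/min.

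**Assumed inputs.** Let m be the number of two-arm patients, all infused over 60 minutes and split 1:1. Then f = (m/2)/110 is the 60-minute share of the final 3600-mg arm and of the placebo arm. Let dA and dP be the added risk at 60 v 120 minutes on 3600 mg and on placebo.

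**Shift from the 120-minute comparison when groups are pooled:**
- 8400 mg minus 3600 mg: −f·dA
- 8400 mg minus placebo: −f·dP
- combined doses minus placebo: (f/2)·dA − f·dP, because m/2 of the 220 active patients had 60 minutes
- 3600 mg minus placebo: both arms carry the same f, so the pooled difference is a weighted average of two like-with-like randomized differences. It is not confounded.

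**8400 minus 3600 mg, in percentage points:**

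| m (assumed) | f | shift if dA = 2 / 5 / 10 | 3600-mg patients left, 110 − m/2 |
|---|---|---|---|
| 30 | 15/110 = 13.6% | −0.3 / −0.7 / −1.4 | 95 |
| 60 | 30/110 = 27.3% | −0.5 / −1.4 / −2.7 | 80 |
| 100 | 50/110 = 45.5% | −0.9 / −2.3 / −4.5 | 60 |

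The shift is zero if m = 0 or dA = 0. Any Russian two-arm patients already on 120 minutes make f smaller for a given m.

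**Example.** Suppose the true risk is 5% on 3600 mg at 120 minutes, 10% on 3600 mg at 60 minutes and 10% on 8400 mg. The pooled 3600-mg risk is 5% + 5f: 5.7%, 6.4% and 7.3% for m = 30, 60 and 100. The true 5-point difference then appears as 4.3, 3.6 and 2.7 points.

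**Planned comparisons with placebo.** If speed matters only for active drug (dP = 0), 8400 mg v placebo does not shift. With dA = 5, combined doses v placebo shifts upward by (f/2)·5 = 0.3, 0.7 and 1.1 points. If speed also matters for placebo, 8400 mg v placebo shifts by −f·dP.

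**Scale.** The 95% half-width for 10% v 5% at 110 per arm is 1.96·√(0.10·0.90/110 + 0.05·0.95/110) = 6.9 points.

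**The case against.** The strongest reply is that no harm is shown. The documents give no count of 60-minute patients and no link between speed and reactions, and Section 1.3.2 reports no infusion-related reactions associated with the antibody so far. That stands. A reader might infer that the 8400 v 3600 mg contrast is biased, or attach a percentage to the bias. The documents do not support either: both needed inputs are missing, and relative percentages also hide the absence of a baseline risk.

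Second, Section 6 names comparisons with standard of care and does not name 8400 v 3600 mg. Section 6.5 names no infusion-reaction rate, and Section 5.3.5.1 records events within 24 hours as separate signs and symptoms. This also stands. The dose comparison is a descriptive one that readers will make. But the named 8400-mg and combined-dose comparisons with placebo have unequal 60-minute shares too.

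Third, every shift in the table is smaller than the 6.9-point half-width, in a trial without formal testing. That limits the weight of the point. The shift is nevertheless systematic, and more patients would not remove it.

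Fourth, Section 6 leaves further detail to the SAP, and the text examined is part 2 of 2 with no separate SAP, so a split made elsewhere cannot be excluded. None appears in the sections shown.

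**Conclusion.** The point holds as a possible distortion of unknown size, confined to acute infusion-related events. It rests on three documented facts: planned duration changed from about 60 to about 120 minutes, two-arm patients remain in the final arms, and safety is grouped by treatment received alone. Whether it matters depends on how many patients had 60 minutes and whether speed affects reactions. If faster infusion of active drug raises risk, the excess of 8400 over 3600 mg is understated: by 0.7 to 2.3 points for an assumed 5-point effect and 30 to 100 two-arm patients. The direction for the comparisons with placebo depends on whether speed also matters for placebo.

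Two further inferences should be resisted. Version 5 does not mark the change everywhere, because the Version 4 log shows it earlier for Russia. And the 3600 mg v placebo comparison is not compromised, since both arms share the same mix of durations.

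**What to change.** Keep the pooled safety table. Add to Section 6.5 one table of suspected infusion-related AESIs and of all events within 24 hours of infusion, by arm and by planned infusion duration. Define planned duration by the protocol version in force at the site when the patient was dosed.

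Do not sort by recorded duration. Section 4.3.2.1 has infusions stopped for some reactions, so a 120-minute infusion cut short would look like a fast one and drop out of the 120-minute rows because of the very event being counted. Recorded times are useful only as a check: "The exact times of study drug administration will be recorded in the relevant" dispensing or administration logs and source notes. That section does not say they are on the case report form, so even the check may need retrieval from source.

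For these events, base comparisons of 8400 mg with 3600 mg and with placebo on patients randomized after the three-arm, 120-minute design opened at their site. This removes the difference in planned duration and keeps the comparison among concurrently randomized patients.

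The cost is one table, the date each protocol version took effect at each site, and fewer comparators: 110 − m/2, or about 95 to 60 per arm on 3600 mg and placebo if 30 to 100 two-arm patients were enrolled (an assumption).
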